## 11. DATA ANALYSIS

### 11.1 Analysis Sets

**Enrolled set (ES):** Defined as all patients screened.

**Treated Set (TS):** All patients who were enrolled in the study and have received at least one dose of Spiolto® Respimat®.

**Per Protocol Set (PPS):** All patients of the TS who have completed the study with no major protocol violation.

### 11.2 Main analysis

Baseline data analysis will be carried out. Comorbidities, [REDACTED] information, and clinical characteristics will be described for the TS.

All categorical variables will be summarized as relative and absolute frequencies. Proportion and 95% CI will be given when appropriate.

The continuous variables will be reported by sample statistics: n (number of observations), number of missing data, mean, standard deviation (SD), minimum, first quartile (Q1), median, third quartile (Q3), and maximum.

Summary statistics will be provided for all primary and secondary endpoints throughout the study.

#### 11.2.1 Analysis of primary outcome.

11.2.1.1 Mean change in patients' quality of life (QoL) according to the total score of COPD Assessment Test (CAT) within three months after the switch from Spiriva® Handihaler® to Spiolto® Respimat®.

The primary estimand is defined as follows:

- A. Population: Is defined through inclusion/exclusion criteria of the study protocol to reflect the target population.
- B. Variable: Continuous variable response.

- C. Intercurrent Event (IE): Include death, drop-out due to any adverse event (AE) and treatment discontinuation. For patients experiencing an IE, the most extreme unfavourable value will be assigned (CAT score at 3 Months equals to 40).
- D. Population level summary: The change from Baseline of total CAT score within 3 Months.

Mixed model for repeated measurements (MMRM) assuming random missingness will be fitted. The dependent variable will be the CAT score at each visit. Visit, GOLD group, smoking habits, packyears, sex, age, and comorbidities appearing at a rate greater than 5% will be entered as covariates. Patients will be fitted at random and an unstructured covariance matrix will be used, allowing adjustment for correlations between study visits within the study patients. The Kenward- Roger degrees of freedom approximation will be used in the model (ddfm=kr).

Summaries of the estimated mean change from baseline of CAT score at 3 Months will be provided with 95% confidence interval. Model information will be provided as footnote under the corresponding table.

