The study will collect data from two visits: baseline (within one week after the time of treatment switch) and approximately at 3 months (± 2 weeks, according to clinical practice) (see [Figure 1](#)). In case of premature discontinuation of Spiolto® Respimat® for any reason (including treatment discontinuation, withdrawal of patient willingness to participate, or unexpected patient problems to continue with the study), an additional unscheduled visit will be performed, if possible according to clinical practice. In this visit, the specific reason for discontinuation will be assessed and all the effectiveness and quality of life variables will be collected as planned for the regular final visit at 3 months (see [Table 1](#)).

Study results will be used to document the effectiveness of Spiolto® Respimat® in reducing the impact of COPD on patient's life. The biggest advantage of the current proposal is that the CAT is a well-known and widespread questionnaire, which is also included in the most recent GOLD guidelines ([1](#)). The CAT questionnaire also exhibits high reproducibility and is independent of various languages, as well ([17,18](#)).

Figure 1. Study scheme

[figure not shown]

Table 1. Visit flow chart and data collection parameters

Parameter	Visit 1 (baseline visit)	Visit 2 (3 months ± 2 weeks after baseline visit)¹	Unscheduled Visit (in case of premature discontinuation)
Informed Consent	X		
Inclusion / Exclusion Criteria	X		
	[REDACTED]	[REDACTED]	
COPD history and clinical characteristics	X	X	X
History of exacerbations in the year before	X		
History of exacerbations since baseline		X	X
Past COPD therapies (12 months before Visit 1)	X		
COPD related and other relevant concomitant medication	X	X	X
Respiratory comorbidities and allergies	X	X	X
Concomitant diseases / Comorbidities	X	X	X
	[REDACTED]	[REDACTED]	
COPD severity based on GOLD assessment ²	X	X	X
COPD Assessment Test (CAT)	X	X	X
EQ-5D-5L questionnaire	X	X	X
Simplified Medication Adherence Questionnaire (SMAQ)		X	X
Modified British Medical Research Council (mMRC) questionnaire	X	X	X
Abbreviated Patient Satisfaction Questionnaire (PASAPQ)		X	X
	[REDACTED]	[REDACTED]	[REDACTED]
Adverse Drug Reactions (serious and non-serious), fatal AEs, pregnancy	X	X	X
Rationale for Spiolto® Respimat® treatment discontinuation (if applicable)		X	X
Continuation or discontinuation of treatment with Spiolto® Respimat® after the study (yes/no)		X	X

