9.2.3 Study visits

The enrolment period of the study will last for a maximum of 9 months. Enrolled patients will undergo two study visits: visit 1 (baseline visit) during screening and enrolment, and visit 2 (follow up visit) 3 months (± 2 weeks) after the baseline visit. Instead of the regular visit 2 at 3-months, an unscheduled visit will take place in case of premature discontinuation to assess the specific reason for discontinuation, to complete main data collection parameters and to check for compliance and safety issues.

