9.7.3 Handling of missing data

The extent of missing data will be evaluated and described.

For the primary analysis, no treatment of missing data is planned except the imputation using the last-observation carried forward [LOCF] method if any post-baseline value is available in patients who discontinued before three months and for whom the value will be set as the last available measure.

Any removal from the analysis will be documented, stating the site and patient number as well as the reason for removal.

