### **5. AMENDMENTS AND UPDATES**

#### **5.1 Changes from protocol analysis**

Additional modifications from the CTP made in this SEAP:

- It was stated in CTP to exclude patients with missing values. Missing values will be treated in a different way according to their nature. Missing values due to Intercurrent Event (IE) are taken care at the estimands definitions, on the other hand, missing values not related to IE will be multiple imputed if missingness is greater than 25% for a specific variable.
- It was suggested in the CTP, [REDACTED]  
[REDACTED]
- To assess the potential associations between patient characteristics, treatment, preference [REDACTED]ing

to health status assessed with CAT will not be assessed via univariate methods, however the applicable [REDACTED] are included to the statistical models in the primary and the first secondary endpoint analysis.

[REDACTED]

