The study will collect data from two visits: baseline (within one week after the time of treatment switch) and approximately at 3 months ( $\pm 2$  weeks, according to clinical practice) (see Figure 1). In case of premature discontinuation of Spiolto® Respimat® for any reason (including treatment discontinuation, withdrawal of patient willingness to participate, or unexpected patient problems to continue with the study), an additional unscheduled visit will be performed, if possible according to clinical practice. In this visit, the specific reason for discontinuation will be assessed and all the effectiveness and quality of life variables will be collected as planned for the regular final visit at 3 months.

**Figure 1.** Study scheme

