### 7.4 STUDY VISITS

The enrolment period of the study will last for a maximum of 6 months. Enrolled patients will undergo two study visits: visit 1 (baseline visit) during screening and enrolment and visit 2 (follow up visit) 3 months ( $\pm 2$  weeks) after the baseline visit. Instead of the

regular visit 2 at 3-months, an unscheduled visit will take place in case of premature discontinuation to assess the specific reason for discontinuation, to complete main data collection parameters and to check for compliance and safety issues.

Visit windowing will be performed as described in Table 7.4:1, in order to assign data to the relevant study visit based on the actual day of the assessment. However, in the listings, all visits performed will be displayed (even if outside time-window).

[figure not shown]
Table 7.4:1 Analysis Visit Window

Analysis visits	Target Day	Analysis visit window [days]
Baseline	1	<=1
3 Months	92	63-121

Safety data are excluded from analysis visit mapping window and the investigator may enter data as needed.

Post baseline: Any assessment after the baseline visit.

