### **10.2 Handling of Missing Values**

If missingness is more than 25% for a specific outcome [REDACTED] methodologies will be examined. More specific information is provided in Section

11.3.1

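### The primary estimand scores every treatment discontinuation as CAT 40, whatever the reason, and the readable SAP does not reconcile this with the protocol's last-observation rule

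*SAP*

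**What the plan says.** **SAP primary estimand (11.2.1.1, item C).** The intercurrent events (IEs) are death, drop-out due to an adverse event, and treatment discontinuation. The rule is: "For patients experiencing an IE, the most extreme unfavourable value will be assigned (CAT score at 3 Months equals to 40". CAT runs from 0 to 40 and higher is worse (SAP 8). Item C does not separate reasons for stopping, and it does not say what happens when a CAT was recorded.

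**Protocol primary analysis (9.7.3).** The last observation is carried forward "if any post-baseline value is available in patients who discontinued before three months". Otherwise, under protocol 9.7, a patient without both CAT scores is left out of the primary analysis.

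**Source of the post-baseline value.** Protocol 9.2.3 states: "Instead of the regular visit 2 at 3-months, an unscheduled visit will take place in case of premature discontinuation". Protocol 9.1 adds that at this visit "all the effectiveness and quality of life variables will be collected as planned for the regular final visit at 3 months". SAP 7.1 keeps the arrangement: "an additional unscheduled visit will be performed, if possible according to clinical practice". Protocol 9.2.4 takes patients out of the study once treatment stops, so this is the only post-baseline CAT planned for them.

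**SAP on the change from protocol.** Section 5.1 describes the protocol rule as exclusion of patients with missing values and continues: "Missing values due to Intercurrent Event (IE) are taken care at the estimands definitions". LOCF is not named in the readable text. SAP 7.4 sets the 3-month window at days 63 to 121, but also defines: "Post baseline: Any assessment after the baseline visit". SAP 10.2 begins "If missingness is more than 25% for a specific outcome" and refers to Section 11.3.1 for detail; that section is redacted.

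**Reasons for stopping.** SAP Table 15.1 lists lack of effect, loss of effect and side effects, but also improved symptoms, inconvenience and cost.

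**The concern.** The two documents can give the same patient very different values. Take a patient with a baseline CAT of 20 who stops because symptoms have improved and scores 12 at the discontinuation visit. Under the protocol the change is 12 - 20 = -8. Under item C as written it is 40 - 20 = +20. For a stop caused by cost or by improvement, the worst possible health status does not describe the patient.

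Both documents define the primary outcome as the mean change in CAT. Each patient given 40 adds a fixed worsening of 40 minus baseline. The headline mean can then depend more on how many patients stopped than on measured health status.

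The instruction is also ambiguous. Item C refers to patients who experience an IE, whereas SAP 5.1 refers to missing values due to an IE. Two programmers could treat a recorded discontinuation CAT differently, above all one taken before day 63.

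The same worst-value rule recurs in SAP 11.2.2 for CAT ≥ 10, EQ-VAS, the EQ-5D-5L dimensions, mMRC, SMAQ and PASAPQ.

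**Working it through.** **1. The plan's own figure.** Protocol 9.5 uses SD 9.0, a two-sided 95% interval, a half-width of at most 0.5 and a coverage probability of 90%. The smallest n with P(t(0.975, n-1) × S/√n ≤ 0.5) ≥ 0.90 is 1310 (probability 0.9007), which agrees with the protocol. The figure does not depend on the IE rule.

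**2. Inputs for the effect of the rule.**
- From the documents: an expected difference of 1.0 and SD of 9.0 (protocol 9.5), and an assigned score of 40 (SAP 11.2.1.1). The protocol gives no direction for the 1.0; it is taken here as an improvement, -1.0.
- Assumed, because the documents give no figure: p, the share of patients with an IE, and B, the mean baseline CAT of those patients (10 to 30).
- Covariate adjustment is ignored.

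**3. Reading A: 40 for every IE.**
Mean change = (1-p)(-1) + p(40-B) = -1 + p(41-B). It is zero at p = 1/(41-B).

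| B | zero at p | p = 2% | p = 5% | p = 10% |
|---|---|---|---|---|
| 10 | 1/31 = 3.2% | -0.38 | +0.55 | +2.10 |
| 20 | 1/21 = 4.8% | -0.58 | +0.05 | +1.10 |
| 30 | 1/11 = 9.1% | -0.78 | -0.45 | +0.10 |

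**4. Reading B: 40 only where no CAT lies in days 63 to 121.**
Let f be the share of IE patients with no in-window CAT, and let the other IE patients change by -1. Mean change = -1 + p·f·(41-B), which is zero at p = 1/[f(41-B)].
- If stops are spread evenly over days 2 to 92, f = 61/91 = 0.67. Zero falls at 4.8%, 7.1% and 13.6% for B = 10, 20 and 30.
- With f = 0.50, zero falls at 6.5%, 9.5% and 18.2%.
- If every recorded CAT is kept, including those before day 63, the formula is the same and f is the share of IE patients with no recorded CAT. The documents do not give that share.

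**5. Comparison with carrying the recorded CAT forward.**
Mean change = -(1-p) + p·L, where L is the mean change at the discontinuation visit. For L from -1 to +2, the mean is -1.00 to -0.85 at p = 5% and -1.00 to -0.70 at p = 10%. Even if every IE patient had worsened by 5, the mean at p = 5% would be -0.95 + 0.25 = -0.70.

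**6. CAT ≥ 10 (SAP 11.2.2.1).**
If every IE patient counts as impaired, the Month-3 proportion is q(1-p) + p, where q is the proportion in the other patients. Both scenarios assume 80% impaired at baseline.
- q = 70%: the crude odds ratio is (0.70/0.30)/(0.80/0.20) = 0.58 with no IEs. At p = 10% the proportion is 0.73, and the ratio is (0.73/0.27)/4 = 0.68.
- q = 78%: the ratio reaches 1 when 0.78 + 0.22p = 0.80, so p = 0.02/0.22 = 9.1%.

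**7. Precision under reading A.**
V = (1-p)·81 + p·7.5² + p(1-p)(41-B)², with an assumed baseline SD of 7.5 in IE patients. The half-width is 1.96·√(V/1500). For B = 30 to 10 it is 0.47 to 0.57 at p = 5% and 0.48 to 0.65 at p = 10%, against 0.455 at p = 0 and a planned maximum of 0.5.

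**The case against.** Assigning the worst value after an IE is a recognised composite strategy. It errs against the product, in an uncontrolled study whose protocol (9.9) itself warns of overestimating the drug effect. For stops due to lack of effect or side effects, an unfavourable value is natural. This stands as a reason to keep the rule as a sensitivity analysis. It does not explain giving the maximum score to stops for cost or improved symptoms, or setting aside a recorded CAT that the protocol uses.

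SAP 5.1 does announce a change in missing-data handling, so the departure is not wholly undisclosed. What the readable text lacks is any mention of LOCF and any statement about recorded scores.

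Observed-data summaries are planned, including Table 6.1.1 for CAT and Table 12.2.1 for preference, which has rows for no preference and for missing answers. Recorded results will therefore be visible beside the estimate. This stands, and it confines the issue to the primary and other IE-rule estimates.

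Parts of SAP 5.1, Section 11.3.1 and the bases of several CAT tables are redacted and may hold an explanation or alternative analyses. That cannot be ruled out, but item C is readable and sets the primary rule.

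Using recorded scores also has a weakness: a CAT taken soon after baseline would stand for Month 3.

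**Conclusion.** The concern holds. As written, item C gives 40 to every death, adverse-event drop-out and treatment discontinuation, which conflicts with protocol 9.7.3, and the readable SAP does not reconcile the two. If 40 goes to all IEs and other patients improve by 1.0, the mean change reaches zero at an IE share of about 3% to 9% for B between 30 and 10 (the higher share for the higher B). At 2% an improvement remains. The effect is smaller if recorded CATs are kept. The share, the baseline of IE patients and the direction of the 1.0 are all assumptions.

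Three stronger readings are tempting but not supported:
- A reader might infer that recorded discontinuation CATs are certainly overwritten. SAP 5.1 speaks only of missing values, and SAP 7.4 counts any later assessment as post-baseline, so an early CAT might be kept. The defect is that the text does not settle this.
- A reader might take the 15% dropout in protocol 9.5 as the IE share or its ceiling. It is neither. Dropout can include reasons that are not IEs, and under LOCF a discontinuer with a recorded CAT stays analysable and need not count as a dropout.
- A reader might infer that CAT ≥ 10 is only weakened, or that it is reversed. The rule pushes towards no improvement; whether it reverses the result depends on the assumed proportions.

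No hypothesis is tested, so what is affected is the reported estimate, its interval and its interpretation. The point should be fixed before analysis.

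**What to change.** 1. In item C of SAP 11.2.1.1, for treatment discontinuation and adverse-event drop-out, use the CAT recorded at the discontinuation visit as the post-baseline value, as in protocol 9.7.3. State that it maps to Month 3 as an exception to Table 7.4:1, and report the day it was taken.
2. Where no such CAT was recorded, leave Month 3 missing in the MMRM already planned. Note that this differs from the exclusion in protocol 9.7.
3. Keep 40 in the primary analysis for deaths only. Report CAT = 40 for all IEs as a named sensitivity analysis.
4. Derive CAT ≥ 10 from the same CAT value. Do not let the IE rule override recorded EQ-VAS, EQ-5D-5L, mMRC or PASAPQ answers. For preference (SAP 11.2.2.7), a recorded answer for Spiolto Respimat or for neither device should not be counted as HandiHaler.
5. In SAP 5.1, name LOCF and state how the analysis departs from it.

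The cost is SAP wording and programming; no new data are needed. There are three downsides. The headline is less conservative. It relies on missing-at-random where no discontinuation visit took place. Early scores may stand for Month 3, so a patient who stops soon after baseline may contribute a change near zero. The retained 40-for-all analysis bounds the contribution of IE patients on the unfavourable side.

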#### **11.2.2.2 Mean change from baseline in the total EQ VAS within three- months after the switch**

Estimand:

- A. Population: Is defined through inclusion/exclusion criteria of the study protocol to reflect the target population.
- B. Variable: Continuous variable response.

C. Intercurrent Event (IE): Include death, drop-out due to any adverse event (AE) and treatment discontinuation. For patients experiencing an IE, the most extreme unfavourable value will be assigned (EQ-VAS equals to 0).

D. Population level summary: The change from Baseline of EQ-VAS score within 3 Months.

This endpoint will be analysed with a Mixed Model for Repeated Measures (MMRM) with EQ-VAS score as dependent variable. Visit, GOLD group, smoking habits, packyears, sex, age, and comorbidities appearing at a rate greater than 5% will be entered as covariates. Patients will be fitted at random and an unstructured covariance matrix will be used, allowing adjustment for correlations between study visits within the study patients. The Kenward- Roger degrees of freedom approximation will be used in the model (ddfm=kr).

Summaries of the estimated mean change from baseline of EQ-VAS score at 3 Months will be provided with 95% confidence interval. Model information will be provided as footnote under the corresponding table

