C. Intercurrent Event (IE): Include death, drop-out due to any adverse event (AE) and treatment discontinuation. For patients experiencing an IE, the most extreme unfavourable value will be assigned (Dyspnea status equals to 4)

D. Population level summary: Mean change of Baseline of Dyspnea status within 3 months

This endpoint will be analysed with a Mixed Model for Repeated Measures (MMRM) with mMRC score as dependent variable. Visit, GOLD group, smoking habits, packyears, sex, age, and comorbidities appearing at a rate greater than 5% will be entered as covariates. Patients will be fitted at random and an unstructured covariance matrix will be used, allowing adjustment for correlations between study visits within the study patients. The Kenward- Roger degrees of freedom approximation will be used in the model (ddfm=kr).

Summaries of the estimated mean change from baseline of mMRC at 3 Months will be provided with 95% confidence interval. Model information will be provided as footnote under the corresponding table

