### 11.2.3 COVID-19 IMPACT

The COVID-19 pandemic started before first patient first visit; it is necessary to analyse the possible impact of the pandemic to this NIS. Separated tables will capture the number of patients dropped-out due to COVID-19, the frequencies of deaths, AEs and SAEs related to COVID-19 and the number of visits delayed/not done due to the pandemic.

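### The primary MMRM ignores intercurrent-event status, so patients known to be event-free but missing at Month 3 are implicitly given a share of the assigned 40s; the shift is small and towards worsening

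*SAP*

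**What the plan says.** SAP 11.2.1.1 defines the intercurrent events as follows: "Include death, drop-out due to any adverse event (AE) and treatment discontinuation". The consequence is: "For patients experiencing an IE, the most extreme unfavourable value will be assigned (CAT score at 3 Months equals to 40". The analysis is then: "Mixed model for repeated measurements (MMRM) assuming random missingness will be fitted. The dependent variable will be the CAT score at each visit". The covariates are visit, GOLD group, smoking, pack-years, sex, age and the more frequent comorbidities. IE status is not among them.

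SAP 5.1 splits missing values in two. Those due to an IE are left to the estimand definition. For the rest, "missing values not related to IE will be multiple imputed if missingness is greater than 25% for a specific variable". At or below 25%, the visible text leaves a non-IE missing Month-3 score to the MMRM.

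The same construction is used for EQ-VAS in SAP 11.2.2.2 ("the most extreme unfavourable value will be assigned (EQ-VAS equals to 0") and for mMRC in SAP 11.2.2.9 ("the most extreme unfavourable value will be assigned (Dyspnea status equals to 4").

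The plan expects some Month-3 values to be missing without an IE. SAP 11.2.3 tabulates "the number of visits delayed/not done due to the pandemic", and SAP Table 7.4:1 maps only days 63 to 121 to Month 3.

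**The concern.** This point accepts the assigned 40 and asks only what happens to the other missing values. A recorded IE patient always has a Month-3 score, namely 40, so the scores still missing when the model is fitted belong to patients without a recorded IE. Because the model does not know who had an IE, it predicts those patients from everyone observed, 40s included.

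For a patient known to be still on treatment and event-free, that contradicts the SAP's own estimand. A patient seen on day 130 is an example: the visit falls outside the window, but treatment status is recorded at Visit 2 (Protocol Table 1). A visit that did not take place is another, provided the site knows the patient's status. The discrepancy does not need informative dropout; it arises even if such visits are missed completely at random. At stake is whether the reported mean change estimates the quantity that the SAP defines.

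**Working it through.** **Inputs from the documents.** Assigned value 40 (SAP 11.2.1.1). CAT runs from 0 to 40 and higher is worse (SAP section 8). Expected change 1.0, SD of change 9.0, half-width 0.5 and dropout 15% (Protocol 9.5).

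**Inputs assumed, because the documents do not give them.** q = share with an IE; m = share known to be event-free but missing at Month 3; mu = mean Month-3 CAT of event-free patients, taken as 14 to 21.

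**The plan's own figures.** The smallest n for a 95% CI half-width of at most 0.5 with 90% probability at SD 9.0 is 1310 (achieved probability 0.9007), as stated. The stated 1507 is 1310 × 1.15. The protocol gives no figure for the effect examined here.

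**Bias for known event-free patients.**

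- Target Month-3 mean: 40q + mu(1 − q).
- One-step MMRM mean: [40q + mu(1 − q − m)]/(1 − m). The weight of the 40s rises from q to q/(1 − m).
- Difference: q × m × (40 − mu)/(1 − m), which is never negative.

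Example with q = 5%, m = 10%, mu = 17. Each missing patient is predicted at 17 + 23 × 0.05/0.90 = 18.28 instead of 17. Averaged over all patients this adds 0.10 × 1.28 = 0.128 CAT points.

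Splitting the 15% loss between q and m gives, in CAT points:

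| q | m | mu = 14 | mu = 17 | mu = 21 |
|---|---|---|---|---|
| 3% | 12% | 0.11 | 0.09 | 0.08 |
| 5% | 10% | 0.14 | 0.13 | 0.11 |
| 7.5% | 7.5% | 0.16 | 0.14 | 0.12 |
| 10% | 5% | 0.14 | 0.12 | 0.10 |
| 12% | 3% | 0.10 | 0.09 | 0.07 |
| 14% | 1% | 0.04 | 0.03 | 0.03 |

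The table treats all non-IE loss as known event-free. Any part with unknown status leaves m and belongs to the last calculation below.

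**Simulation check.** 2,000 runs of 1,500 patients, baseline mean 20, change −1, two-visit likelihood estimator. The bias was 0.117 at 5%/10%, 0.130 at 7.5%/7.5% and 0.111 at 10%/5%. The formula with mu = 19 gives 0.117, 0.128 and 0.111. The bias vanished when q or m was 0. Borrowing only from event-free patients left at most 0.002. One mixed model fitted to 20,000 simulated patients (7.5%/7.5%) gave 0.115 against 0.127 from the formula.

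**Scale against the 40 rule.** The rule itself moves the mean by q(40 − mu) = 0.05 × 23 = 1.15 in the example. The extra shift is m/(1 − m) of that, or 11%.

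**EQ-VAS.** At q = 5%, m = 10% and an assumed mean of 65: 0.05 × 0.10 × (0 − 65)/0.90 = −0.36 points, again towards worsening.

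**Missing patients with unknown status.** Now let m be missing patients of unknown status, of whom a share r had an unrecorded IE. The one-step bias is m(40 − mu)[q/(1 − m) − r]. At q = 5%, m = 10%, mu = 17 this is 2.3 × (0.0556 − r): zero at r = 5.6% and −0.22 at r = 15%. Treating all of them as event-free gives −m × r × (40 − mu), which is −0.13 at r = 5.6%.

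**The case against.** The strongest reply is that nobody can tell from the visible text who is event-free. Treatment discontinuation is an IE without limit on its reason. Protocol 9.1 and SAP 7.1 describe premature discontinuation of Spiolto broadly enough to include a patient's withdrawal of willingness. SAP Table 1.1 lists loss to follow-up and consent withdrawal beneath a line on treatment discontinuation, with the row hierarchy lost. On a broad reading most of the 15% becomes IE, m falls to the few missed or out-of-window visits, and the bias falls towards 0.03. This stands, and the lower rows of the table reflect it.

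A reader might infer that random missingness is false by design for every missing patient and that the error always runs against Spiolto. The documents do not support that. A patient lost with unknown treatment status may have had an IE, and then some share of the 40s is appropriate. The last calculation shows that the sign can reverse, and that an event-free imputation would err in Spiolto's favour.

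Three further limits hold. Early leavers may have values from the unscheduled visit, and the protocol's LOCF rule (9.7.3) is not visibly withdrawn, so m may be smaller. SAP 10.2 sends missing-data detail to the redacted 11.3.1, and the table shells show several CAT estimates on redacted bases. The 1.0 change and 0.5 half-width predate the 40 rule: in the example, with baseline 18, the target change is −1 + 1.15 = +0.15, not a one-point improvement.

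None of this reaches patients whose event-free status is known.

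**Conclusion.** The point holds for Month-3 scores missing in patients known to be event-free. For them the one-step MMRM departs from the SAP's estimand, and the shift is towards worsening. The size is about 0.03 to 0.16 CAT points at 15% total loss. Against the protocol's planning figures that is 3 to 16% of the 1.0 change and 6 to 32% of the 0.5 half-width, but these are rough benchmarks only. The effect is second order next to the 40 rule.

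The conclusion rests on assumed q, m and mu, and on reading 11.2.1.1 as fitting the model to the 40-filled scores. That is the natural reading, since the assignment would otherwise have no role in the estimate, but no sentence says so. For patients with unknown Spiolto status no direction can be claimed. Redacted 11.3.1 may already deal with part of this. Multiple imputation above 25% missingness would have the same weakness unless it conditions on IE status.

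**What to change.** In SAP 11.2.1.1, 11.2.2.2 and 11.2.2.9:

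1. State whether loss to follow-up and consent withdrawal count as an IE.
2. For patients known to be event-free, model or impute missing Month-3 values from event-free patients only, using baseline score and covariates. Then assign the worst value to IE patients and average over everyone. For CAT, the Month-3 mean is (1 − q) × event-free model mean + q × 40. Take the CI from Rubin's rules or a patient bootstrap.
3. For patients with unknown treatment status, report both the event-free imputation and the current one-step MMRM, or a range of assumed IE shares, as sensitivity analyses.

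If 11.3.1 already conditions on IE status, a cross-reference from 11.2.1.1 is enough. The cost is SAP wording and some extra programming, with no new data. The downside is a CI that no longer comes directly from the MMRM.
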